| | | | | |
| VI. References | | | | |
| | | | | |
| Evidence based committee (Reviewers) | | | | |
| Name | | Signature | Date | |
| 1. | | | | |
| 2. | | | | |
| | | | | |
| Research plan committee | | | | |
| | | | | |

| Name | Signature | Date |
|------|-----------|------|
| 1. | | |
| 2. | | |

Administrative information:

1. Title:

Comparative Clinical Evaluation of Partial Coverage CAD/CAM Restoration Versus Nanohybrid Composite of Carious Hypomineralized Permanent Molars: A Randomized Controlled Trial.

2. Protocol Registration:

3. Protocol version:

4. Funding: Self-funded

University Responsibilities: All contribute in initiated the study design, will generate random sequence, contribute in clinical work, provide statistical expertise in clinical trial design and make the final edited of the article.

II. Introduction:

5. Background and rationale:

Hypomineralization of carious permanent molars is defined as qualitative defects caused by disruptions in either the calcification or maturation phases of amelogenesis. (1)

Statement of the problem:

Conventionally, stainless steel crowns were used for those molars. However, due to the need for esthetics and the young age of patients, it was necessary to look for a cosmetic and conservative restoration alternative. (2) Partial coverage restorations were recommended as a substitute for crowns to maintain teeth healthy. It is considered a minimally invasive approach. (3)

The rationale for conducting the research:

Conventional restoration for such hypomineralized molars necessitates massive removal of the tooth structure to receive full coverage crowns that cause more biologically harmful consequences like pulp exposure especially in young permanent teeth and aggressive tooth structure loss (4). To fulfill the biological criteria for tooth preparation, conservatism is the major notion and goal that dental practitioners strive to achieve. Nowadays, minimally invasive techniques are frequently employed to

support this idea. To meet the growing need for conservative and esthetics tooth restorations, partial coverage ceramic restorations are becoming more necessary. These CAD/CAM restorations show satisfactory mechanics, restoring function, and esthetic with preserving tooth structure (5)

Since all materials used to treat such cases have distinct chemical compositions, they have different properties that affect their clinical outcome. Therefore, it is essential to compare them clinically because any restoration's clinical outcome affects its long-term success. According to the null hypothesis, different materials would not significantly affect the clinical result of ceramic overlay restorations.

Patients in all groups will receive a minimally invasive restoration with high esthetic advantages (Protection of the weak cusps and elimination of carious lesions with an esthetic way out) and long-term success of their affected carious hypomineralized permanent molars (IPS e.max CAD or Direct nanohybrid flowable composite) that require minimal preparation depends on the type of restoration will receive.

Aim of the study:

This randomized controlled trial study will evaluate the clinical success of direct nanohybrid flowable composite versus IPS e.max CAD Partial Coverage.

Research question:

Are the direct nanohybrid flowable composite and IPS e.max CAD Partial Coverage clinically successful materials in restoring the carious Hypomineralized Permanent Molars?

PICOS:

P: Patients suffer from hypomineralized permanent molars

I: Direct nanohybrid flowable composite

C: IPS e.max CAD

O: Clinical Success (aesthetics, functional and biological criteria))

II. Methods

Study Design:

Study design: Randomized Controlled Trial

Estimated Enrolment: 48 Carious Hypomineralized Permanent Molars

Allocation: Randomized

Intervention Model: Parallel Assignment

Primary Purpose: Restorations Hypomineralized Permanent Molars

Official Title: Comparative Clinical Evaluation of Partial Coverage CAD/CAM Restoration Versus Nanohybrid Composite of Carious Hypomineralized Permanent Molars: A Randomized Controlled Trial.

Estimated Study Start Date: December 2023 [Time frame: 12 months] Estimated Primary

Completion Date: January 2025

Trial design:

The study is a randomized controlled trial (RCT) where 2 arm parallel groups with a 1:1 allocation ratio were compared. The child participants and the legal guardian of each participating child and the statistician were blinded.

Outcome Measures:

1. **Primary outcome:** Clinical success [Time Frame: 12 months].

- According to FDI World Dental Federation criteria **[Appendix A]**
- There were three assessment categories (aesthetics, function, and biological), each with five subcategories. From best to worst, the subcategories were:
(1) clinically excellent, (2) clinically good, (3) clinically sufficient, (4) clinically not sufficient but repairable, and (5) clinically unacceptable. Assessment with category (5) was rated as a clinical failure.
- At the follow-up visits over one year at (baseline “1 day “, 6 and 12 months) after cementation., will take standardized photographs and the restorations will clinically evaluate by an independent and calibrated clinician.

Eligibility Criteria

Ages Eligible for Study: Above 6 Years

Sexes Eligible for Study: All

Accepts Healthy Volunteers: Yes

Criteria

Inclusion Criteria:

1. Above 6 years old
2. Cooperative children with large carious First Permanent Molars (FPM) lesions associated with weak cusps and defected hypo-mineralized enamel.
3. Apparently healthy patients.
4. Patients will be available to be clinically reviewed up to 1 year

Exclusion Criteria:

1. Patients with Symptoms of pulpitis.
2. Patients with uncontrolled active tooth decay or periodontal disease (i.e. 4+ mm probing depth and bleeding on probing).
3. Poor oral hygiene and motivation.
4. Patients with parafunctional habits (e.g., bruxism, biting on hard objects).
5. Patients with debilitating illnesses or complicating medical conditions

Explanation regarding the choice of comparators:

IPS e.max CAD: Till now, glass-ceramic-based restorations still offer the best translucency and esthetic qualities. The novel generation of lithium disilicate-based materials as IPS e.max CAD provides standard thickness and quick fabrication. Moreover, the adhesive technique used with this restoration type significantly raises its mechanical properties. (6)

Beautifil Flow Plus X (Shofu) is a bioactive flowable nano-hybrid restorative with a newly developed patented nanofiller. It is indicated for all classes including occlusal and cusp. It has all the Giomer Technology attributes, anti-bacterial, acid neutralization, and fluoride release and recharge, with improved handling and effortless polishing, and maintains a long-lasting shine. Beautifil Flow Plus X has the strength, durability, and aesthetics of a hybrid composite. (7)

Sample size (Power analysis):

Sample size calculated depending on a previous study (Alaa M. Eldehna a et al., 2023) as reference. (8) According to this study, the probability of surface gloss as an aesthetics criterion in group 1 is 0.96. If the estimated probability of group 2 is 0.6, we will need to study 20 cases in each group with probability (power) 0.8. The Type I error probability. We used the chi-squared test to evaluate that was performed by using P.S.Power 3.1.6. Total sample size increased to 24 subjects per group to compensate for a 15 % drop out. Sample size calculation was achieved using chi-squared test to evaluate that was performed by using P.S. Power3.1.6, software Version 3.1.2 (Vanderbilt University, Nashville, Tennessee, USA).

Statistical Methods

Statistical analysis:

Data was collected, tabulated, and statistically analyzed using Microsoft Excel ® 2016, Statistical Package for Social Science (SPSS)® Ver. 24. And Minitab ® statistical software Ver. 16.

Handling of numerical / quantitative variables:

Numerical data will be explored for normality by checking the data distribution using Kolmogorov-Smirnov and Shapiro-Wilk tests. Data will be presented as mean & standard deviation. If data will

be normally distributed comparison between 2 different groups will be performed by using independent t-test, comparison between 2 related groups will be performed by using Paired t-test, while comparison between more than 2 groups will be performed by using One Way ANOVA test followed by Tukey's Post Hoc test for multiple comparisons. If data will be non-parametric data comparison between 2 different groups will be performed by using Mann-Whitney test, comparison between 2 related groups will be performed by using Wilcoxon Signed Rank test, while comparison between more than 2 groups will be performed by using Kruskal-Wallis test.

Handling of categorial / qualitative variables:

Data will be presented as frequency and percentages. All comparisons will be performed by using Chi square test.

Recruitment:

The study will be conducted at the pediatric dentistry department of MSA University pediatric outpatients. All subjects will be monitored and reviewed at day 1 after 6 months and 12 months.

Post-trial care

- Oral hygiene instructions and serving brush and toothpaste
- Dietary recommendations

Patients Guardians Consent and Ethical Approval

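### Does counting enrolment in molars but sample size in subjects break the independence that the planned tests assume?

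*Combined protocol and SAP*

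**What the plan says.** The plan counts its sample in three ways. Study Design counts teeth: "Estimated Enrolment: 48 Carious Hypomineralized Permanent Molars". The sample size section first counts cases, "we will need to study 20 cases in each group with probability (power) 0.8", and then people: "Total sample size increased to 24 subjects per group to compensate for a 15 % drop out".

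On design, Study Design has "Intervention Model: Parallel Assignment" and Trial design says "The study is a randomized controlled trial (RCT) where 2 arm parallel groups with a 1:1 allocation ratio were compared". Neither names the child or the molar as the unit allocated. The rationale places patients in groups and gives each a single restoration: "Patients in all groups will receive a minimally invasive restoration".

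The relevant inclusion criterion is "Cooperative children with large carious First Permanent Molars (FPM) lesions associated with weak cusps and defected hypo-mineralized enamel". It sets no maximum number of study molars per child and no rule for choosing among several.

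For categorical outcomes, "All comparisons will be performed by using Chi square test". For numerical outcomes the between-group tests are the independent t-test or Mann-Whitney. No method for clustered data is mentioned.

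**The concern.** Hypomineralisation can affect more than one first molar in the same child, and the inclusion criterion uses the plural. A team recruiting towards a target counted in molars might enter two from one child. Those molars share diet, hygiene and bite, so their outcomes are likely to be correlated. If both went to the same arm, 24 molars would carry less information than 24 independent observations. The listed tests would not allow for this, and their false-positive rate would rise above the nominal level.

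**Working it through.** **1. The plan's own sample size.** Inputs from the sample size section: rates 0.96 and 0.60, power 0.80, drop-out 15%. The visible text gives no value for the type I error, so two-sided 0.05 is assumed. With mean rate 0.78, the uncorrected chi-square formula gives

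n = [1.96 × √(2 × 0.78 × 0.22) + 0.842 × √(0.96 × 0.04 + 0.60 × 0.40)]² / 0.36² = (1.148 + 0.444)² / 0.1296 ≈ 19.6, so 20 per group.

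Drop-out: 20 / 0.85 = 23.5, so 24 per group. Both stated figures reproduce, and both rest on independent observations.

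**2. What the two totals imply.** Subjects: 2 × 24 = 48. Molars: 48. Every enrolled child has at least one study molar, so 48 molars among 48 children means exactly one each. If k children per arm gave two molars and the arm still held 24 molars, it would contain 24 − k children. For k = 2, 4, 6 and 12 that is 22, 20, 18 and 12, each below the stated 24.

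**3. Size of the effect if the plan were not followed.** The number of molars per child and the within-child correlation (ICC) are not in the documents. The illustration assumes two molars for some children and ICC 0.3 to 0.5. With whole children randomised, the design effect is 1 + (Σm²/Σm − 1) × ICC, where m is the number of molars a child contributes. The last column is the simulated false-positive rate of the uncorrected chi-square test (beta-binomial outcomes, 24 molars per arm, rate 0.78, 400,000 trials).

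| Children per arm giving two | Σm²/Σm | Design effect, ICC 0.3 / 0.5 | False-positive rate, ICC 0.3 / 0.5 |
|---|---|---|---|
| 0 of 24 | 24/24 = 1 | 1 / 1 | 0.054 |
| 2 of 22 | 28/24 = 1.17 | 1.05 / 1.08 | 0.059 / 0.064 |
| 4 of 20 | 32/24 = 1.33 | 1.10 / 1.17 | 0.065 / 0.073 |
| 6 of 18 | 36/24 = 1.5 | 1.15 / 1.25 | 0.071 / 0.085 |
| 12 of 12 | 48/24 = 2 | 1.30 / 1.50 | 0.093 / 0.119 |

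The large-sample approximation 2 × [1 − Φ(1.96/√design effect)] gives 0.086 and 0.110 for the last row, close to the simulated values.

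**4. The same departure under other units of allocation.**
- If molars are randomised individually, chance decides where each molar goes, whatever child it came from. At rate 0.78 the simulated false-positive rate is about 0.052 to 0.054, the same as under independence.
- If every child gives two molars, one to each arm, the variance of the difference shrinks by the factor 1 − ICC. The approximation 2 × [1 − Φ(1.96/√(1 − ICC))] gives about 0.019 at ICC 0.3 and 0.006 at ICC 0.5. Simulation gives 0.022 and 0.008, so the test is conservative.

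**5. The primary outcome.** Only an FDI score of 5 counts as clinical failure, so success may well be high. At an assumed success rate of 0.95 with whole children randomised, the false-positive rate is 0.018 with one molar each, 0.025 to 0.029 if 4 of 20 children give two, and 0.038 to 0.053 if all do. There is no material inflation.

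**The case for a change.** The strongest reply is that an implied rule is not an instruction. The figure labelled as enrolment is in molars, and a clinician who sees a child with two eligible molars is not told whether to enter both, choose one, or split them between arms. If the choice were made after allocation, it could itself bias the comparison. Because even the direction of any error depends on the unit allocated, there is a case for naming that unit. One sentence would do so at no cost to the sample size.

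The factual part stands. No visible text states one molar per child, a selection rule or the unit of randomisation. Some pages, including the consent form, were not available, so this can be said only of the visible text.

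It does not show that the plan is wrong. Counting two molars from one child within the 48 would contradict the stated 24 subjects per group, so the plan's own figures already exclude it. Nothing in the plan says that the molar is chosen after allocation. A team reading both totals would enter one molar per child, and the listed tests would then be appropriate.

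**Conclusion.** No change follows. The plan uses different words for the same count: 48 molars and 48 subjects agree only at one molar per child, which also fits the parallel-group design and the single restoration per patient. Followed as written, the observations are independent and the chi-square, t-test and Mann-Whitney comparisons are valid on this point.

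Harm would need two departures together: fewer than 24 children per arm with some giving two molars, and allocation of whole children. Under the assumed ICC of 0.3 to 0.5, with 2 to 6 such children per arm, the false-positive rate would be about 0.059 to 0.085 instead of 0.054, and only for mid-range outcomes such as surface gloss, the criterion used for sizing. The extreme case, in which every child gives two, reaches 0.093 to 0.119 but halves the planned number of children. At an assumed success rate of 0.95 the primary outcome is not materially affected. The ICC, the number of molars per child, the 0.95 rate and the two-sided 0.05 level are assumptions. The conclusion on one molar per child rests only on the plan's two totals.

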Appendix A: FDI World Dental Federation criteria

| Properties | Parameters | Excellent Score 1 | Good Score 2 | Satisfactory Score 3 | Mediocre Score 4 | Poor Score 5 |
|-----------------|--|---|---|---|--|--|
| Esthetic | Surface lustre | Luster comparable to enamel | Slightly dull; some isolated pores | Dull surface; multiple pores ($>1/3$ of the surface) | Rough surface; presence of voids | Very rough surface |
| | Marginal and Surface staining | No staining | Minor staining | Moderate staining | Pronounced staining | Severe staining |
| | Anatomical form | Ideal form | Form slightly deviated | Moderate changes of form | Pronounced changes of form | Lost of form |
| Functional | Fracture of material and retention | No fractures or cracks | Small hairline cracks | Two or more larger hairline cracks and/or chipping (not affect marginal integrity) | Chipping fractures, bulk fractures with or without partial loss (less than half of the restoration) | Partial or compete loss of restoration |
| | Marginal adaptation | Harmonious outline, no gaps | Marginal gaps ($<150 \mu\text{m}$); small marginal fractures | Marginal gaps ($>150 \mu\text{m}$ and $<250 \mu\text{m}$); several marginal fractures | Marginal gaps $>250 \mu\text{m}$ or dentin/base exposed; severe marginal fractures | Restoration lost but in situ ; generalized major gaps |
| | Radiographic examination* | No pathology | Adhesive pooling and/or slightly internal maladjustment of the restoration | | Evidence of secondary caries; apical pathology; fracture or loss of restoration or tooth | |
| Biological | Postoperative (hyper) sensitivity and tooth vitality | No hypersensitivity; normal vitality | Minor hypersensitivity for a limited period of time (<1 week); normal vitality | Moderate hypersensitivity for a limited period of time (>1 week and <6 months); mild sensitivity, no complains | Intense hypersensitivity; cold sensitivity with minor subjective symptoms | Acute pulpitis or non vital tooth; endodontic treatment is mandatory |
| | Recurrence of caries | No secondary or primary caries | Small and localized demineralization area | Larger areas of demineralization with no dentin exposure | Localized and accessible caries with cavitation | Deep secondary caries with exposed dentin |

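### Clinical success is never defined, and Score 4, which the plan calls not sufficient, falls outside its only failure rule

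*Combined protocol and SAP*

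**What the plan says.** Under Outcome Measures the primary outcome is "Clinical success [Time Frame: 12 months" on the FDI criteria in Appendix A, with visits at baseline (day 1), 6 and 12 months. Aesthetic, functional and biological properties are graded from 1 (best) to 5 (worst). Score 3 is the last grade described as sufficient. The two grades below it, and the one classification rule that follows them, read "4) clinically not sufficient but repairable, and (5) clinically unacceptable. Assessment with category (5) was rated as a clinical failure".

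Appendix A shows what Score 4 contains. For recurrence of caries it is "Localized and accessible caries with cavitation". For fracture and retention it includes "bulk fractures with or without partial loss (less than half of the restoration". For marginal adaptation it covers gaps above 250 µm "or dentin/base exposed; severe marginal fractures". On the aesthetic side, pronounced staining and a rough surface with voids are also Score 4.

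No sentence defines success, says where Score 4 belongs, or says how the parameter grades combine into one result per tooth. Statistical Methods assigns the chi-square test to all categorical comparisons and does not name the primary one. The sample size section uses another quantity: "the probability of surface gloss as an aesthetics criterion in group 1 is 0.96", against an assumed 0.6 in the other group.

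**The concern.** The wording of the scale puts the limit of sufficiency between Scores 3 and 4. The failure rule puts its limit between Scores 4 and 5. Score 4 lies between the two with no assigned status, and the primary outcome is named after the one category that has no definition.

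The research question asks whether the two materials are clinically successful in carious hypomineralized molars. A molar with new cavitated caries, or with part of its restoration lost, is not a failure under the only rule given. Whoever computes success as 100% minus the failure rate will count that molar as a success. Whoever uses Scores 1-3 will not. The plan allows both, so the choice could be made after the grades are known, and the headline percentage and the comparison between arms could change with it.

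**Working it through.** **1. The two limits side by side**

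| Score | Status by the scale's wording | Status by the failure rule |
|---|---|---|
| 1-3 | excellent, good, sufficient | not failure |
| 4 | not sufficient, repairable | not failure |
| 5 | unacceptable | failure |

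Only the Score 4 row differs.

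**2. Effect on the success rate.** Assume one grade per tooth; the plan does not say how that grade is formed. Let s1 to s5 be the shares of teeth at each grade in one arm.

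- Success as not failed: A = s1 + s2 + s3 + s4 = 1 − s5
- Success as sufficient: B = s1 + s2 + s3
- Difference: A − B = s4 ≥ 0

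Within an arm the difference can only go one way. One Score 4 tooth is worth 1/20 = 5.0 percentage points with 20 evaluable teeth and 1/24 = 4.2 points with 24. Three such teeth out of 20 (an illustration, not a forecast) would separate the two success rates by 15 points.

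**3. Effect on the comparison of arms.** The difference between arms changes by s4(arm 1) − s4(arm 2). This can have either sign, so the ambiguity need not favour one material, but it can change the size of the contrast.

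**4. The plan's own sample size.** Inputs: 0.96 and 0.6, power 0.80, 15% dropout (sample size section). No alpha value is given, so 0.05 two-sided is assumed. With mean proportion 0.78 and no continuity correction:

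n = [1.960·√(2·0.78·0.22) + 0.842·√(0.96·0.04 + 0.6·0.4)]² / 0.36² = (1.148 + 0.444)² / 0.1296 = 19.6, rounded up to 20 per arm.

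Dropout: 20 / 0.85 = 23.5, rounded up to 24 per arm and 48 in total. The plan's figures reproduce. They answer a question about surface gloss and a 36-point difference, and say nothing about Score 4 or Score 5 rates.

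**5. Whether the choice of limit settles power.** All rates here are assumed. Power is exact for the uncorrected chi-square test at two-sided 0.05, with 24 per arm:

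| Assumed failure rates | Difference (points) | Power |
|---|---|---|
| 2% vs 10% | 8 | 14.1% |
| 5% vs 13% | 8 | 14.5% |
| 10% vs 18% | 8 | 12.8% |
| 5% vs 20% | 15 | 36.5% |
| 5% vs 30% | 25 | 68.7% |
| 2% vs 27% | 25 | 79.1% |

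At a fixed difference of 8 points, more events bring no gain. At 25 points the lower base rate does better. Power here follows the assumed difference, so moving the limit to Scores 4-5 helps only if the arms differ more on that outcome, which the documents do not show.

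**The case against.** The strongest reply is that the label and the failure rule are compatible. Score 4 is repairable and Score 5 is not, so Score 4 can be a legitimate intermediate grade. A reader might infer that the plan counts Score 4 restorations as successes. The documents do not say so; that needs the extra step of equating success with not failed. This part of the reply stands. It leaves the gap open, because the primary outcome is success and no status is given to a grade described as not sufficient.

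The chi-square test might also be meant for the distribution of grades on each parameter, as sizing on surface gloss would suggest. Score 4 would then be visible in the tables. That is possible, but the plan does not state it, and clinical success would still need a definition.

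A reader might further infer that a Score 5 outcome leaves too few events to compare the arms. That is conditional. If Score 5 occurred in 2% of both arms, the chance of no failure in 40 teeth would be 0.98^40 = 45%. With none in one arm, chi-square needs 4 in the other to reach p < 0.05, at 20 or at 24 per arm. At 4% vs 40%, however, power would be 86% with 20 per arm. The documents give no rate that would decide between these cases.

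Finally, requiring Scores 1-3 on every parameter would deny success to an otherwise sound tooth for pronounced staining or a rough surface alone. This is a fair argument against imposing that rule as the sole primary definition.

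**Conclusion.** The point holds as a gap in the definition of the primary outcome. Success is undefined and Score 4 is unclassified, although Score 4 includes serious functional and biological findings. If success is computed as not failed, it exceeds the share at Scores 1-3 by exactly the Score 4 share: 5.0 points per tooth at 20 per arm, 4.2 at 24. The direction is certain on that reading. The total size is unknown, because no Score 4 rate is given.

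The conclusion assumes one grade per tooth. It does not depend on any assumed event rate. No lack of events is demonstrated, and no gain in power is claimed for counting Score 4. Worth correcting before the grades are analysed.

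**What to change.** 1. In Outcome Measures, state how each score counts towards success, for each parameter and for the tooth as a whole. Say how the parameter grades are combined and how a tooth repaired before 12 months is counted in the analysis.
2. In Appendix A, reconcile the fracture and retention row: partial loss of less than half appears under Score 4, while the Score 5 cell covers partial loss without a size limit. As it stands, the same tooth could be graded either way.
3. In Statistical Methods, pre-specify the 12-month comparison of Scores 4-5 versus 1-3 beside the Score 5 failure comparison. Name one as primary and the other as a key sensitivity analysis.
4. Report Score 4 (repair needed) and Score 5 (failure) separately by arm, and do not describe Score 4 restorations as successes in the conclusions.
5. Show the results by aesthetic, functional and biological category as well, so that a purely aesthetic Score 4 can be told apart from caries or fracture.

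Cost: protocol and SAP wording plus a few table rows. The grades are already collected, and no treatment or visit changes. Reported success rates may be lower, and a rule covering every parameter will include purely aesthetic shortfalls, hence item 5. The sample size would still rest on surface gloss. Its adequacy for the chosen outcome should be stated with expected rates and an alpha level, neither of which the plan now gives for success or failure.

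### The only stated power is for surface gloss, one of ten FDI parameters; the plan gives no rate, power or detectable difference for 12-month clinical success, its primary outcome

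*Combined protocol and SAP*

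**What the plan says.** The Outcome Measures section of the combined protocol and SAP names one primary outcome, "Clinical success [Time Frame: 12 months"], assessed on the FDI criteria. The PICOS list describes it as "Clinical Success (aesthetics, functional and biological criteria"). The only failure rule is "Assessment with category (5) was rated as a clinical failure". Appendix A lists ten rated parameters. Surface lustre is one; others are fracture and retention, marginal adaptation, recurrence of caries, and sensitivity and vitality.

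The Sample size (Power analysis) section takes its rates from gloss: "the probability of surface gloss as an aesthetics criterion in group 1 is 0.96. If the estimated probability of group 2 is 0.6". It concludes that "we will need to study 20 cases in each group with probability (power) 0.8", and raises this to 24 per arm for 15% dropout. Alpha has no value; the text reads "The Type I error probability. We used the chi-squared test".

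The rationale states the null hypothesis that "different materials would not significantly affect the clinical result of ceramic overlay restorations". For categorical data the plan is: "Data will be presented as frequency and percentages. All comparisons will be performed by using Chi square test". It mentions no confidence interval.

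**The concern.** A reader will naturally take the stated power of 0.8 as the power of the primary comparison. It belongs to a different event. Under the failure rule a molar fails on a score of 5. A gloss probability of 0.96 or 0.60, with no statement of which lustre score it refers to, does not give the frequency of that event in either arm. If the parameters are instead compared one at a time, the calculation covers one of ten.

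What is at stake is the meaning of a non-significant result. With percentages and a chi-square p-value alone, nothing in the planned report would show how large a difference in success remains compatible with the data.

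**Working it through.** **Inputs from the plan.** Gloss rates 0.96 and 0.60; power 0.80; chi-squared test; 1:1 allocation; 15% dropout; 20, then 24, per arm.

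**Inputs assumed.** Alpha two-sided 0.05, because the plan leaves it blank. Success read as no score 5 on any parameter at 12 months. Better-arm success rates from 0.80 to 1.00, because the plan gives none.

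**1. Reproducing the plan's figure.** With p̄ = (0.96 + 0.60)/2 = 0.78,

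n = [1.96·√(2·0.78·0.22) + 0.8416·√(0.96·0.04 + 0.60·0.40)]² / 0.36² = (1.148 + 0.444)² / 0.1296 = 19.56, so 20 per arm.

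Then 20/0.85 = 23.5, so 24. Other readings of the blank alpha do not give 20: one-sided 0.05 gives 16, two-sided 0.05 with continuity correction gives 25, and one-sided 0.05 with correction gives 21.

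**2. Detectable difference in clinical success at 20 per arm.** For each assumed better-arm rate p₁, solve the same formula for p₂ with n = 20. Check for p₁ = 0.90, p₂ = 0.507: p̄ = 0.7035; 1.96·√(2·0.7035·0.2965) = 1.266; 0.8416·√(0.09 + 0.250) = 0.491; (1.266 + 0.491)²/0.393² = 20.0.

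Lower-arm rate that gives 80% power:

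| Assumed better arm | Planning formula | Gap (points) | Exact, uncorrected chi-square | Exact, Fisher |
|---|---|---|---|---|
| 1.00 | 0.688 | 31 | 0.74 | 0.69 |
| 0.96 | 0.605 | 36 | 0.63 | 0.58 |
| 0.90 | 0.507 | 39 | 0.52 | 0.47 |
| 0.80 | 0.377 | 42 | 0.37 | 0.33 |

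The exact columns enumerate both binomial distributions. The method must be named when a figure is quoted: at 20 per arm, 0.96 vs 0.60 has power 0.81 by the planning formula, 0.86 by exact uncorrected chi-square and 0.76 by Fisher.

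**3. Power for smaller gaps.** Exact uncorrected chi-square at 20 / 24 per arm: 0.96 vs 0.85, 0.18 / 0.24; 0.90 vs 0.80, 0.14 / 0.17; 0.80 vs 0.70, 0.11 / 0.13. For any 10-point gap with the better arm between 0.80 and 1.00, the range is 0.11 to 0.15 at 20 per arm and 0.13 to 0.22 at 24. By Fisher at 20 per arm it is 0.04 to 0.07.

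**4. What a non-significant result would leave open.** Take 20/20 vs 18/20 successes.
- Pooled rate 38/40 = 0.95, so χ² = 0.10²/(2·0.95·0.05/20) = 2.105 and p = 0.15. Expected failures are 1 per arm, and Fisher's p is 0.49.
- Wilson limits are 0.839 to 1.000 and 0.699 to 0.972.
- Newcombe limits are 0.10 − √(0.161² + 0.072²) = −0.077 and 0.10 + √(0² + 0.201²) = 0.301.
- The difference is 10 points, with a 95% interval from −8 to +30.

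**The case against.** **Gloss is not foreign to the primary outcome.** It is an esthetic parameter of the same FDI instrument, and the PICOS outcome includes aesthetics. If the parameters are compared one by one, which the analysis section does not rule out, the calculation does address part of the primary outcome. This stands: the sizing is incomplete, not unrelated.

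**The rates in the working are assumed.** This also stands. They illustrate a range and are not estimates for these materials. A reader might infer that the trial is shown to be underpowered for clinical success. The documents do not support that, because they give neither an expected rate nor a difference that would matter. What they support is that power for this outcome is unstated.

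**Success as no score 5 on any parameter is an interpretation.** The failure rule does not say how ten parameter scores combine into one result per molar.

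**The plan never says that non-significance will be read as equal performance.** A reader might infer an equivalence aim from the null hypothesis, but that is an ordinary null of no difference. The case for a confidence interval rests on what the report would show, not on any misreading the plan proposes.

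**The blank alpha looks clerical.** Two-sided 0.05 without correction reproduces 20, and the other readings listed in the working do not. It still has to be written in.

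**Conclusion.** The point holds in this form: the stated power of 0.8 at 20 per arm applies to surface gloss, one component of the primary outcome, and the plan states no rate, power or detectable difference for 12-month clinical success. It should not be read as saying that 20 or 24 is miscalculated; both reproduce under two-sided 0.05 without continuity correction.

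Under that alpha, the no-score-5 reading and better-arm rates of 0.80 to 1.00, the planning formula gives detectable gaps of 31 to 42 points at 20 per arm. The exact chi-square figures run from 26 points (1.00 vs 0.74) to 43 (0.80 vs 0.37). The choice of method moves the lower-arm rate by several points but does not change the conclusion that only large differences would be detected reliably.

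**What to change.** Keep 24 per arm, the primary outcome and the 12-month time frame.

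1. In Sample size (Power analysis), state that the 80% power applies to surface lustre only, and complete alpha and sidedness.
2. In the same section, add the difference in 12-month clinical success detectable with 80% power at 20 evaluable molars per arm. Use the same planning formula as the existing figure and label the rates as assumptions: 1.00 vs 0.69, 0.96 vs 0.60, 0.90 vs 0.51, 0.80 vs 0.38 (two-sided 0.05). If exact power is quoted instead, name the test, since chi-square and Fisher differ.
3. In Outcome Measures, state how the parameter scores combine into success or failure per molar. No score 5 on any parameter at 12 months is one interpretation of the failure rule, for the sponsor to confirm.
4. In Statistical Methods, report the 12-month difference in success proportions with a 95% confidence interval, for example Newcombe's, alongside the test.

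The cost is rewording, with no extra patients. The downside is that the stated power for the primary outcome becomes less favourable.
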